#### **7.1.6. *Code breaking***

Not applicable.

#### **7.1.7. *Destruction***

If needed, destruction of vaccine doses will follow standard practice at each trial site. The number of vials and their lot numbers will be documented.

### **7.2. *Auxiliary medicinal products***

Not applicable.

#### **7.2.1. *Dose and administration***

Not applicable.

#### **7.2.2. *Drug accountability and treatment compliance***

Not applicable.

### **7.3. Concomitant use of other medicinal products and treatments**

Medications considered necessary for the safety and well-being of the participant may be provided at the discretion of the investigators, unless otherwise specified in the exclusion criteria. Concomitant medication should be recorded in the Case Report Form (CRF).

### **7.4. Treatment after trial end**

Not applicable.

## **8. Methods for measurement of endpoints for clinical efficacy and safety**

### **8.1. Methods for measurement of endpoints for clinical efficacy**

An overview of all planned laboratory assays can be found in section 5.3.3. (Table 4).

#### ***8.1.1. Methods for the primary endpoint***

The primary endpoint of this trial is defined as the descriptive analysis of the differences in RSV A and B neutralizing antibodies at D31 after prime vaccination in the two age groups enrolled in this study. The primary endpoint will be measured in serum by an established neutralization assay. The assays will be performed at accredited laboratories of GSK. The analysis will be performed after the collection of all D31 samples. A short description of the method can be found in section 16.

### 8.1.2.

### *Methods for the exploratory endpoints*

[REDACTED]

## 8.2. Methods for measurement of endpoints for clinical safety

To assess reactogenicity of the vaccine, all solicited AEs will be recorded over the 4-day follow-up period after each vaccination. The AEs will be reported by the study participants on standardized diary cards and information will be collected by the respective study personnel. Solicited AEs include:

- Injection site pain
- Injection site erythema
- Injection site swelling
- Fever (similar definition as described in section 6.2.)
- Headache
- Fatigue
- Myalgia
- Arthralgia

Grading of intensity of solicited AEs will follow the description in section 18.2.

To assess safety, all unsolicited AEs with an onset during the 30-day follow-up period after each vaccination (i.e., the day of vaccination and 29 subsequent days) will be recorded.

To assess safety, any SAEs or pIMD will be recorded from the day of vaccination until up to 6 months after vaccination.

Fatalities will be recorded throughout the whole study period.

## **9. Handling Adverse Events**

### **9.1. Definitions**

#### **9.1.1. *Adverse Event (AE)***

Any untoward medical occurrence in a participant to whom a medicinal product is administered and which does not necessarily have a causal relationship with this treatment.

#### **9.1.2. *Adverse Reaction (AR)***

The phrase “reaction” to a medicinal product means that the causal relationship between the medical product and an adverse event is at least a reasonable possibility, that is the relationship cannot be ruled out.

#### **9.1.3. *Serious Adverse Event (SAE)***

Any untoward medical occurrence that at any dose requires inpatient hospitalization or prolongation of existing hospitalization, results in persistent or significant disability or incapacity, results in a congenital anomaly or birth defect, is life-threatening, or results in death.

Medical and scientific assessment will be made to determine if an event is serious. A list of SAEs that have been excluded from reporting in this study are registered in section 9.3.

#### **9.1.4. *Suspected Unexpected Serious Adverse Reaction (SUSAR)***

An adverse reaction/event that is unexpected, serious, and suspected to be caused by the treatment, i.e. adverse reactions/events that are not included in the RSI section of the Investigator's Brochure (IB) or SmPC.

### **9.1.5.**

### ***Potential immune-mediated diseases (pIMD)***

Adverse events of special interest (AESIs) collected during this study include potential immune-mediated diseases (pIMDs). No other AESIs will be collected. pIMDs are a subset of AESIs that include autoimmune diseases and other inflammatory and/or neurologic disorders of interest which may or may not have an autoimmune etiology. AEs that need to be recorded and reported as pIMDs include those listed in Table 5 (see section 18).

## **9.2. Assessment of Adverse Events (AE)**

### ***9.2.1. Assessment of causal relationship***

The investigator is responsible for determining whether there is a causal relationship between the AE/SAE and use of the investigational medicinal product.

Consideration should be given to whether there is a reasonable possibility of establishing a causal relationship between the adverse event and the investigational medicinal product based on the analysis of the available evidence. All AEs can be categorized as either related (yes) or not related (no).

Those AEs which are suspected of having a causal relationship to the investigational medicinal product will be followed up until the participant has recovered or is stabilized and on the way to good recovery (see also section 9.3.). If the reporting investigator does not provide any information on causality, the sponsor should consult with the reporting investigator and encourage the expression of a position on this issue. The sponsor must take into account the assessment of causality provided by the investigator. If the sponsor disagrees with the investigator's assessment of causality, both the investigator's and the sponsor's views should be included in the report.

### **9.2.2.**

### ***Assessment of intensity***

Each adverse event shall be classified by an investigator as mild, moderate or severe. Assessment of intensity of solicited AEs is described further in section 18.2.

**Mild:** The adverse event is relatively tolerable and transient in its nature but does not affect the participant's normal life.

**Moderate:** The adverse event causes deterioration of function but does not affect health. The event can be sufficiently unpleasant and interferes with normal activities but does not completely obstruct them.

**Severe:** The adverse event causes deterioration of function or work ability or poses a health risk to the participant.

#### **9.2.3. *Assessment of seriousness***

The investigator is responsible for assessing the seriousness (serious or non-serious). If the adverse event is considered serious, this should be reported as a serious adverse event (SAE) by the investigator to the sponsor.

### **9.3. *Reporting and registration of Adverse Events***

Reporting of AEs will follow standard procedures, including follow-up on reactogenicity for 4 days after each vaccination for systemic and local solicited adverse events. Unsolicited AEs are reported for 30 days following each vaccination while SAEs are reported for 6 months following each vaccination. Follow-up of fatalities is carried out throughout the whole study period.

AEs that occur during the trial and not excluded from follow-up, which are observed by the investigator/trial nurse or reported by the participant will be registered in the CRF regardless of whether they are assessed as related to the investigational medicinal product or not. Assessment of causal relationship,

severity, and whether the AE is considered to be an SAE will be made by the investigator directly in the CRF (RedCap) or on a trial-specific worksheet. At minimum, for each AE/SAE, a description of the event is recorded (diagnosis/symptom if diagnosis is missing), start and stop dates, causal relationship, severity, if the AE is considered to be an SAE, measures and outcome.

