#### **4.5. Secondary endpoint(s)**

The secondary endpoints are:

- Occurrence, intensity and duration of solicited AEs in the study participants at the administration site and solicited systemic AEs with an onset during the 4-day follow-up period after each vaccination (i.e., the day of vaccination and 3 subsequent days).

- Occurrence of unsolicited AEs in the study participants with an onset during the 30-day follow-up period after each vaccination (i.e., the day of vaccination and 29 subsequent days).
- Occurrence of SAEs in the study participants from the day of vaccination until 6 months. However, certain conditions will be excluded from this monitoring, to ensure that reporting is focused on relevant safety issues. The decision for this is based on the overall higher prevalence of certain conditions in the older age group. This includes but is not limited to falls, fractures, and the onset of tumors. A list of events that can be excluded is explicitly defined in the study protocol (see section 9.3.2). Such events are considered expected in an older patient population (>80 years). These do not need to be reported as SAEs unless there is an indication of a relationship with the investigational drug.
- Occurrence of pIMDs in the study participants from the day of vaccination until 6 months. A list of possible conditions that could qualify as pIMDs is added in section 18.
- Occurrence of any fatal SAEs in the study participants from Day 1 up to study end.

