### ***9.3.2. Reporting of Serious Adverse Events (SAE)***

Serious Adverse Events (SAE) are reported to the sponsor on a special SAE form within 24 hours of the investigator being informed of the SAE.

Follow-up information describing the outcome and handling of the SAE is reported as soon as this information is available. The original SAE form should be kept in the Investigator Site File.

Duplicate reporting will be avoided by reporting to one of the entities. This process will be conducted according to the standard clinical routine.

Reporting of the following list of conditions will not be recorded as these conditions are commonly occurring in the studied age group:

- Falls and fractures even if they would, by definition, qualify as SAE (i.e. if they would lead to hospitalization, prolonged hospitalization or disability)
- Onset of cancers and tumors
- Dementia and dementia related delirium or confusion unless they are related to AEs following vaccination (e.g. in case of fever-induced delirium) and would qualify as SAE

- Bacterial or fungal infections

To assess safety, any fatal SAEs will be recorded from the day of vaccination until the end of the study period.

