### **9.3.3. *Reporting of Suspected Unexpected Serious Adverse Reactions***

Those SAE which are assessed by sponsor to be SUSAR are to be reported to the EudraVigilance database. The completed CIOMS form will be the basis for the reporting, by the Swedish Medical Products Agency in the EudraVigilance database according to the specified time frames.

Any SAE/pIMD must be reported to the sponsor as soon as possible and not later than 24 h after the site has become aware of the SAE. SUSAR that are fatal or life-threatening are reported as soon as possible and no later than 7 days after the SAE/pIMD has become known to the sponsor. Relevant follow-up information is sent thereafter within an additional 8 days. Other SUSAR are reported as soon as possible and no later than 15 days after they have come to the sponsor's knowledge.

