### **10.4. *Sample size calculations***

This study is primarily designed to gather descriptive immunogenicity data in older adults upon vaccination with Arexvy, including adults of 80 years of age and older for which data is currently limited. As the study objective is purely descriptive rather than to demonstrate efficacy or test a hypothesis, no formal power-based sample size calculation has been made.

A sample size of 30 individuals in the 60-65 years group and of 35-40 individuals in the 80+ years group was chosen based on feasibility of recruitment, clinical judgement and a 10-20% drop-out expected in the older age group. This sample size of approximately 30 individuals per age group is expected to generate valuable immunogenicity data in an otherwise understudied population and to allow for exploratory comparisons between age groups. Given the descriptive nature of the study, its findings will be interpreted as preliminary.

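### Table 1 schedules no adverse-event check at the 3-month visit, so about 83% of the dose-1 SAE/pIMD window lies between two scheduled checks although participants attend in person within that gap

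*Protocol*

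**What the plan says.** **The window.** SAEs and pIMDs are secondary endpoints. Section 4.5 lists "Occurrence of pIMDs in the study participants from the day of vaccination until 6 months" and gives SAEs the same period. Section 8.2 says that "any SAEs or pIMD will be recorded from the day of vaccination until up to 6 months after vaccination". Section 9.3 gives the period per dose: "Unsolicited AEs are reported for 30 days following each vaccination while SAEs are reported for 6 months following each vaccination". It names SAEs but not pIMDs in that sentence.

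**The schedule.** Table 1 in section 5.2 has an Adverse Events column. After dose 1 it is ticked at V1 (day 0), V3 (day 7), V4 (day 31, ±3 days) and V6 (6 months, ±14 days). V5 (3 months, ±14 days) has a single tick, under Blood draw. Tables 2 and 3 confirm V5 as a sampling visit. After dose 2 the ticks fall at V7, V9, V10 (day 31) and V11 (6 months), with no visit between V10 and V11.

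**Reporting outside the ticked visits.** Section 9.3 covers AEs "which are observed by the investigator/trial nurse or reported by the participant will be registered in the CRF", without tying this to a visit. SAEs go to the sponsor "within 24 hours of the investigator being informed of the SAE" (section 9.3.2), and section 9.3.3 adds: "Any SAE/pIMD must be reported to the sponsor as soon as possible and not later than 24 h after the site has become aware".

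**The concern.** The participant is on site about halfway through the SAE/pIMD window, and the schedule does not tell the site to ask about safety. The empty cell carries meaning, because Table 1 uses this column to plan ascertainment: V11 has an Adverse Events tick and no blood draw, so it is a contact held for safety alone.

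The exposure is greatest for pIMDs that are not serious. Unsolicited AEs count only with onset on the day of vaccination or the 29 days after it. Beyond that, a non-serious event enters the data only if it is recognised as a pIMD. Table 5 includes gout, psoriasis, polymyalgia rheumatica, Raynaud's phenomenon and thyroiditis. A participant who comes for a blood draw has little reason to volunteer these as trial events. Missed events lower the count, and events learned of late may be misdated.

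The loss need not be equal between groups. Section 6 enrols the older group from long-term care facilities and the younger group from the community, at a different site. What staff observe and what participants report may therefore differ with age group, and section 10.2.1 reports safety counts and percentages for both groups.

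**Working it through.** The protocol gives no figure for the interval between checks, so there is none to reproduce. The check is arithmetic on Table 1.

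**Inputs**
- V4: day 31 ±3, so day 28 to 34 (Table 1).
- V6: 6 months ±14 days (Table 1). Taking 6 months as 183 days is an assumption; V6 is then day 169 to 197.
- V5: 3 months ±14 days (Table 1), taken as day 91, so day 77 to 105.

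**Current gap between scheduled checks (V4 to V6)**
- Nominal: 183 − 31 = 152 days. Share of the window: 152/183 = 83.1%.
- With 6 months as 180 days: 149/180 = 82.8%. The day count hardly matters.
- Over the V4 tolerance: (183 − 34)/183 = 81.4% to (183 − 28)/183 = 84.7%.
- Gap in days with both tolerances: 169 − 34 = 135 to 197 − 28 = 169.

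**Gap with a check at V5**
- Nominal: 91 − 31 = 60 days, then 183 − 91 = 92 days.
- Longest possible: 197 − 77 = 120 days.
- Reduction of the longest gap: nominal (152 − 92)/152 = 39%; worst case against worst case (169 − 120)/169 = 29%.

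**Timing of the 24-hour report.** The duty in sections 9.3.2 and 9.3.3 starts when the site becomes aware. An event before V5 that nobody observes or volunteers would first be sought at V6, nominally 92 days later than a check at V5 would allow.

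**Drop-out between months 3 and 6.** Section 10.2.2 expects 10–20% drop-out among 35–40 older participants. If this is spread evenly over 18 months (an assumption), the number leaving in these three months is 35 × 0.10 × 3/18 = 0.58 to 40 × 0.20 × 3/18 = 1.33. This counts people who leave, not events lost. For an event to be lost, such a person must also have had an SAE or pIMD between day 31 and month 3, not reported it, and missed the safety follow-up visit in section 6.3. The expected number of lost events by this route is a small fraction of 0.58 to 1.33.

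**The case against.** The strongest reply is that the 6-month window and the visit schedule do different jobs. Sections 4.5, 8.2 and 9.3 define which events count, and Table 1 plans the prompts. A check at V6 that covers the time since V4 is compatible with the window, so the sections do not contradict each other. That stands.

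A reader might also infer that 83% of the window rests on one retrospective question at month 6. The protocol does not support this. Section 9.3 registers events observed or volunteered at any time, including at V5, and sections 9.3.2 and 9.3.3 set a 24-hour duty for SAEs and pIMDs. What remains is that these routes depend on someone noticing: the 24-hour duty does not create awareness, and a scheduled check does. Where passive follow-up alone is intended, the protocol says so, as section 9.7 does for infections. It makes no such statement for SAEs or pIMDs.

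Poor recall in the older group should not be overstated either. Section 6.1 excludes any history of dementia and conditions that moderately or severely impair cognition, and care-facility staff could learn of admissions and deaths without a trial visit. This weakens the argument for serious events. It does little for non-serious pIMDs.

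Finally, AE checks now fall at day 0, day 7, day 31 and 6 months after both doses. A check at V5 alone breaks that symmetry and leaves the equally long dose-2 gap as it is. This is a real but small cost. No readable objective compares safety between doses (the exploratory objectives are blacked out), and the dose-2 gap contains no existing visit to use.

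**Conclusion.** The point holds as a gap in scheduled ascertainment. About 152 of 183 days of the dose-1 window (83%; 135 to 169 days with tolerances) lie between the checks at V4 and V6. They are covered by spontaneous reporting, staff observation and the V6 check, while an in-person visit within the gap goes unused for safety.

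The interval rests on Table 1 and the 183-day convention. How many events would be missed cannot be estimated from the protocol, and a claim that SAEs are materially under-counted would go beyond it. Unequal capture between age groups is a possibility that follows from the two settings; it has not been shown.

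Nothing in the primary immunogenicity analysis is affected. The trial is descriptive, and "no formal power-based sample size calculation has been made". This is a low-cost improvement to two secondary safety endpoints, worth making because the visit already exists. The visit schedule belongs in the protocol, so the matter cannot be left to the statistical analysis plan.

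**What to change.** 1. In Table 1, tick Adverse Events at V5 (3 months).
2. In section 9.3, state that SAEs, pIMDs and fatal events since the last contact are asked for at V4, V5 and V6 after dose 1, and that V6 remains the contact that closes the 6-month endpoint.
3. In the eCRF, flag events first learned of at V5. Show any dose 1 versus dose 2 safety summary with and without them, because dose 2 has no 3-month visit.

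The cost is a few minutes at a visit that already takes place, one repeated eCRF form, one tick in a table and one sentence of text. No new visit is needed.

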### ***9.3.1. Reporting of Adverse Events (AE)***

All AEs shall be registered in the CRF within 3 days as indicated above (section 9.3, Reporting and registration of Adverse Events).

### ***9.3.2. Reporting of Serious Adverse Events (SAE)***

Serious Adverse Events (SAE) are reported to the sponsor on a special SAE form within 24 hours of the investigator being informed of the SAE.

Follow-up information describing the outcome and handling of the SAE is reported as soon as this information is available. The original SAE form should be kept in the Investigator Site File.

Duplicate reporting will be avoided by reporting to one of the entities. This process will be conducted according to the standard clinical routine.

Reporting of the following list of conditions will not be recorded as these conditions are commonly occurring in the studied age group:

- Falls and fractures even if they would, by definition, qualify as SAE (i.e. if they would lead to hospitalization, prolonged hospitalization or disability)
- Onset of cancers and tumors
- Dementia and dementia related delirium or confusion unless they are related to AEs following vaccination (e.g. in case of fever-induced delirium) and would qualify as SAE

- Bacterial or fungal infections

To assess safety, any fatal SAEs will be recorded from the day of vaccination until the end of the study period.

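### Section 9.3.2 drops listed events from recording without the relatedness exception that section 4.5 gives the same list, so a related non-fatal SAE could go unrecorded

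*Protocol*

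**What the plan says.** Section 4.5 (Secondary endpoints) counts SAEs for 6 months and takes some conditions out of that monitoring. It locates the list elsewhere: "A list of events that can be excluded is explicitly defined in the study protocol (see section 9.3.2". The reason given is age: "Such events are considered expected in an older patient population (>80 years". It then sets a condition: "These do not need to be reported as SAEs unless there is an indication of a relationship with the investigational drug".

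Section 9.3.2 holds the list. Its lead sentence reads: "Reporting of the following list of conditions will not be recorded as these conditions are commonly occurring in the studied age group". Four bullets follow:

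- "Falls and fractures even if they would, by definition, qualify as SAE"
- onset of cancers and tumours
- "Dementia and dementia related delirium or confusion unless they are related to AEs following vaccination", with the further requirement that the event qualify as an SAE, and with delirium brought on by fever as the example
- bacterial or fungal infections

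The section closes by saying that "any fatal SAEs will be recorded from the day of vaccination until the end of the study period".

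Section 9.1.3 points to the exclusion: "A list of SAEs that have been excluded from reporting in this study are registered in section 9.3". Section 9.3 has AEs registered whether or not they are judged related, but only those not removed from follow-up. Section 9.3.3 requires any SAE or pIMD to reach the sponsor within 24 hours and does not mention the list.

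**The concern.** The two sections govern the same list and give different instructions. Under 4.5 a listed event may be left out of SAE reporting only while no link to the vaccine is indicated. Under 9.3.2 it is not recorded at all, and for three bullets nothing brings it back. Because one bullet has its own exception, a reader may take its absence from the others as deliberate.

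At stake is whether a suspected-related, non-fatal serious fall, fracture, tumour or bacterial or fungal infection enters the SAE endpoint as 4.5 defines it, and whether it is assessed as a possible SUSAR. Sections 9.1.4 and 9.6 judge expectedness against the reference safety information in the product label. The 4.5 rationale that such events are usual at that age therefore does not settle SUSAR status. A statistical analysis plan cannot repair this, since it cannot recover events that sites never entered.

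**Working it through.** No formula applies. The check sets the passages side by side.

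**1. Same list?** Yes. Section 4.5 names 9.3.2 as the place where the list is defined.

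**2. Does each bullet in 9.3.2 carry the 4.5 exception?**

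| 9.3.2 bullet | Exception in 9.3.2 | Same as 4.5? |
|---|---|---|
| Falls and fractures | none; out even when serious | no |
| Cancers and tumours | none | no |
| Dementia, related delirium or confusion | linked to AEs after vaccination, and serious | different condition |
| Bacterial or fungal infections | none | no |

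Count: 4 bullets, of which 3 have no exception, 1 has a different one and 0 have that of 4.5. The lead sentence has none either.

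**3. Do other sections supply it?**

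- 9.1.3 points to the exclusion without the condition.
- 9.3 limits registration to AEs not excluded, so its rule of registering regardless of relatedness does not restore listed events.
- 9.2.1 makes the investigator responsible for judging causality of AEs and SAEs, and 9.2.3 sends serious events to the sponsor. Neither mentions the list.
- 9.3.3 requires any SAE or pIMD within 24 hours, again without mentioning the list. Read with 9.3.2, this is a further mismatch: one section demands every SAE, and the section just before it says some are not recorded.

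**4. What is lost on a literal reading of 9.3.2?** A listed event that is serious, non-fatal and suspected to be related. Fatal SAEs are recorded to study end, and pIMDs have their own endpoint.

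**5. Over what time?** SAEs are reported for 6 months after each of two vaccinations: 2 × 6 = 12 months of about 18 per participant, in 65–70 participants.

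**6. Which participants?** Section 4.5 justifies the list only for those over 80. Section 9.3.2 speaks of one studied age group, although two are enrolled (60–65 years, and 80 years or older). Whether the list applies at 60–65 is not stated.

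**The case against.** The best defence is that a site has good grounds to report a related listed event anyway. Section 4.5 defines the endpoint and could be read as governing. Sections 9.2.1 and 9.2.3 provide the causality and seriousness judgements, and 9.3.3 imposes the 24-hour duty without qualification. This stands as mitigation. It does not remove the conflict, because 9.3.2 is the operational instruction on SAE reporting and says the opposite. The defence is hardest to sustain for falls and fractures, which 9.3.2 removes even when serious.

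Four stronger readings are tempting but not supported:

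- *Related events will be lost, because the 4.5 exception has no step at which to operate.* The judgement step exists in 9.2.1 and 9.2.3. What is unclear is whether 9.3.2 overrides it.
- *Four sections conflict.* The substantive conflict is between 4.5 and 9.3.2. Sections 9.1.3 and 9.3 only point to or apply an exclusion whose terms are set elsewhere.
- *The dementia bullet discards vaccine-caused confusion.* That depends on one way of parsing it. The fever example shows that vaccine reactions are meant, and confusion unrelated to dementia may not be on the list at all. A history of dementia is also an exclusion criterion. What stands is that its condition differs from that of 4.5.
- *The list also cuts the unsolicited-AE endpoint.* Section 8.2 records all unsolicited AEs and does not mention the list. This is an ambiguity, not a demonstrated loss.

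It is also fair that the SAE endpoint is secondary and descriptive.

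**Conclusion.** The inconsistency between 4.5 and 9.3.2 is certain on the text: none of the four bullets carries the 4.5 exception. Its consequence is possible, not established. It needs a listed event that is serious, non-fatal and suspected to be related, at a site that follows 9.3.2 literally in preference to 4.5 and 9.3.3. The protocol gives no rate for such events, so no number lost is claimed. The scope over the two age groups is ambiguous rather than contradictory. This should be fixed: it concerns which safety data are collected, and events not recorded at the time may not be recoverable at analysis.

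**What to change.** Reconcile 9.3.2 with 4.5, using the protocol's own condition:

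1. In the lead sentence of 9.3.2, state that a listed condition is still recorded and reported as an SAE when a relationship with the vaccine is indicated, so that this covers all four bullets.
2. Align the dementia and delirium bullet with that condition.
3. Have 9.1.3 refer to the exception.
4. Leave the 24-hour duty in 9.3.3 unqualified for suspected-related events. Tying it to the list could weaken it.
5. State whether the list applies to both age groups.

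Unrelated listed events can stay excluded. No separate causality entry is needed for each one: in a cohort enrolled from long-term care, recording every fall and infection would largely undo the exclusion. The cost is a few sentences of wording and a short site instruction, submitted as a protocol change under section 13. The only added data collection is for listed SAEs with a suspected link, which 4.5 already keeps reportable.

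### Section 9.3.2 stops the recording of four condition types in wording broader than the exclusion it implements, leaving the age group and the AE/SAE scope unsettled

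*Protocol*

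**What the plan says.** Section 4.5 places the exclusion inside the SAE endpoint. Its reason is age: "The decision for this is based on the overall higher prevalence of certain conditions in the older age group". It adds: "Such events are considered expected in an older patient population (>80 years". The consequence it draws is that such events need not be reported as SAEs, unless a relationship with the vaccine is indicated. It refers to section 9.3.2 for the list. Section 9.1.3 likewise describes the list as one of SAEs.

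Section 9.3.2 introduces the list with: "Reporting of the following list of conditions will not be recorded as these conditions are commonly occurring in the studied age group". The items include "Falls and fractures even if they would, by definition, qualify as SAE", "Onset of cancers and tumors" and "Bacterial or fungal infections". The remaining item is dementia and related delirium or confusion, the only one with its own exception (events linked to AEs after vaccination that would qualify as SAEs). Fatal SAEs are still recorded to the end of the study.

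The unsolicited-AE endpoint in section 4.5 carries no exclusion: "Occurrence of unsolicited AEs in the study participants with an onset during the 30-day follow-up period after each vaccination". Section 8.2 calls for all such events to be recorded, and section 9.3.1 for all AEs to be entered in the CRF within 3 days. Section 9.3 registers "AEs that occur during the trial and not excluded from follow-up".

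**The concern.** The rule that sites will apply is section 9.3.2, and it is wider than its justification in two ways.

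- **Age.** The reason given concerns people over 80. The rule has no age limit, and it refers to a single age group in a trial that enrols two.
- **Endpoint.** The exclusion belongs to the SAE endpoint. The rule says the conditions are not recorded at all, which reaches the unsolicited-AE endpoint as well.

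SAE and unsolicited-AE occurrence are both secondary endpoints, and section 10.2.1 reports them as counts and percentages by age group. An event that was never entered in the CRF cannot be restored by any later analysis. Section 6 enrols the 60-65 group at one site and the ≥80 group at another. If the two sites read the rule differently, the resulting difference in recording cannot be separated from a difference between age groups.

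**Working it through.** The plan states no figure to reproduce, so the check is mainly a comparison of the sections.

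| Protocol section | What it governs | Age limit | Reach |
|---|---|---|---|
| 4.5, SAE endpoint | Waiver of SAE reporting | Reason given for the older group, >80 years | SAEs only; related events kept |
| 9.1.3 | Definition of SAE | None stated | Calls the list a list of SAEs |
| 9.3.2 | The list itself | One unspecified age group | Listed conditions not recorded; fatal SAEs kept |
| 4.5 and 8.2, unsolicited AEs | 30-day endpoint and its method | None | All unsolicited AEs, no exclusion |
| 9.3 | General CRF registration | None | AEs not excluded from follow-up |
| 9.3.1 | AE registration | None | All AEs, with a reference back to 9.3 |

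**Step 1, age.** The SAE endpoint covers the study participants without distinction, and nothing in 9.3.2 exempts the 60-65 group. Group sizes are in section 10.2.2: 30 in the 60-65 group and 35-40 in the older group, 65-70 in total. The share of participants to whom the stated reason does not apply is 30/70 = 42.9% to 30/65 = 46.2%.

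**Step 2, endpoint.** The wording on falls and fractures excludes them even when they are serious, which implies that non-serious ones are excluded too. The tumour and infection items carry no seriousness qualifier. Taken literally, a non-serious fall or bacterial infection within 30 days of vaccination is both to be recorded (8.2, 9.3.1) and not to be recorded (9.3.2). Section 9.3 does not settle this: its restriction may refer to the list or to the follow-up windows set out just before it. Section 9.3.1 points back to 9.3, so it does not settle it either.

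**Step 3, confounding.** With one site per age group, how a site reads the rule and which age group it enrols are the same variable. If one site follows 9.3.2 literally and the other follows 8.2, the by-group percentages differ even when the true incidences are equal.

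**Step 4, size.** The documents give no event rates, so the total undercount cannot be estimated. For one participant whose only event goes uncounted, the change in incidence is 1/n:

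- 60-65 group: 1/30 = 3.3 percentage points
- ≥80 group: 1/40 = 2.5 to 1/35 = 2.9 percentage points

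**The case against.** The strongest reply is that the sections, read together, already give the narrow rule. The list stands under a heading on SAE reporting, 4.5 speaks of reporting as SAEs, and 9.1.3 calls it a list of SAEs. The one age group in 9.3.2 can be taken as the older cohort, since 4.5 refers to that list and gives the older group as its reason. The restriction in 9.3 can be taken as meaning the time windows. The exclusion is also deliberate and openly stated.

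Much of this stands, and it rules out three stronger readings that a reader might infer:

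- **That the list certainly applies to the 60-65 group.** The text allows this reading but does not state it. The age scope is ambiguous.
- **That listed events certainly vanish from the unsolicited-AE count.** Sections 8.2 and 9.3.1 say the opposite, so this is a contradiction and not a settled removal.
- **That listed events never reach a causality assessment.** Section 4.5 keeps events with an indicated relationship, and section 9.2.1 assigns causality to the investigator. The documents do not support the claim.

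The loss is also narrower than four complete categories. Fatal SAEs are kept, and only bacterial and fungal infections are listed, not viral ones.

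The reply does not remove the defect. The operative sentence concerns recording, not only reporting as an SAE, and a site that follows it literally complies with the protocol. A separate statistical analysis plan could define the counts but could not recover events missing from the CRF.

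**Conclusion.** The point holds as an internal inconsistency. Section 9.3.2 is broader than the exclusion in 4.5 and conflicts with 8.2 and 9.3.1, and 9.3 leaves the conflict open. On a literal reading, non-fatal listed events in the 60-65 group go unrecorded without the stated justification, and listed events drop out of the 30-day unsolicited-AE endpoint.

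Two descriptive secondary safety endpoints are exposed; the primary endpoint is not. The per-participant shift of 3.3 percentage points in the 60-65 group assumes a denominator of all 30 participants and a person with no other counted event. How many such people there would be is unknown. The confounding arises only if the two sites read the rule differently, which the present wording permits. The protocol should be corrected, because the repair is small and cannot be made after data collection.

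**What to change.** Reconcile sections 4.5, 8.2, 9.1.3, 9.3, 9.3.1 and 9.3.2. In 9.3.2, state that:

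1. the list waives SAE reporting only, and only in the ≥80 group, as 4.5 justifies;
2. listed events with onset in the 30-day window after each vaccination are still registered in the CRF as unsolicited AEs, in both age groups.

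In 9.3, say what the restriction on follow-up refers to: the list or the time windows.

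The cost is protocol wording and some extra CRF entries among 65-70 participants. The waiver of SAE reporting for expected events in the older group is preserved. Showing SAE incidence with and without listed events is optional, and would require the listed serious events to be entered in the CRF.
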